3.1. General Description

IMCgp100-401 is a rollover study that is designed to provide continued access to IMCgp100 for eligible patients with advanced melanoma who have previously participated in study IMCgp100-01 (the parent study). Parent studies that are eligible for patients to continue to receive IMCgp100 in this rollover study must have completed and satisfied their primary endpoints or have been terminated by the Sponsor for reasons other than safety.

This rollover study will enroll patients who are currently receiving IMCgp100 treatment and for whom the parent IMCgp100 clinical study completes. At the time of parent study completion, the rollover study will enroll all patients actively receiving IMCgp100 treatment in the parent study in order to continue to provide these patients access to treatment. Patients who enroll in the rollover study will, in the opinion of the investigator, continue to receive clinical benefit from treatment with IMCgp100. Patients who are receiving treatment as part of an ongoing and not yet completed study, are not eligible to participate in the rollover study until the time of study completion.

At the time of rollover study entry, each patient will be assigned to the appropriate dosing cohort based on the parent study dosing regimen, cohort and the recommendation of the Sponsor and principal investigator. Changes to the dosing cohort from the parent study to the rollover study must be approved in writing by the Sponsor prior to enrolling the patient in the rollover study. See Table 6-1 in Section 6.1 of the study protocol for details of Dose and

Document:	...\Immunocore\IMCgp100\YXA43404\Biostatistics\Documentation\SAP\IMCgp100-401_SAP_v1.0.docx	Version Number:	v1.0
Author:	[name]	Version Date:	09MAY2019

Template No: CS_TP_BS016 Revision 4
 Effective Date: 01Apr2016

Reference: CS_WI_BS005

Treatment Schedule of this rollover study. All patients must sign the rollover study consent form and be enrolled in the new study. All assessments will commence with Rollover Cycle 1 (RC1). Safety assessments (physical examinations, clinical laboratory, and electrocardiogram (ECG) assessments, as well as continuous monitoring of AEs) will continue throughout the study at the described intervals. Patients will continue to receive IMCgp100 until loss of clinical benefit for the individual patient (as per local imaging standard of care and the appropriate response criteria, as defined by the principal investigator), unacceptable toxicity as defined by the principal investigator or Sponsor, withdrawal of consent, loss to follow-up, or death.

3.2. Schedule of Events

Schedule of events can be found in Section 7 of the protocol.

3.3. Changes to Analysis from Protocol

The following are documented changes to analysis from protocol:

- Tables/Listings for change from baseline and shift tables are removed from the analysis for vital signs and ECG data. Note that vital signs will only be collected at baseline.

4. Planned Analyses

A final analysis after database lock is planned for this study.

4.1. Final Analysis

All final, planned analyses identified in this SAP will be performed by IQVIA Biostatistics following Sponsor Authorization of this SAP, Database Lock, and Analysis Sets and associated output shells.

5. Analysis Sets

Agreement and authorization of patients included/excluded from each analysis set will be conducted prior to the final analysis of the study.

5.1. All Patients Enrolled Set [ENR]

The All Patients Enrolled (ENR) set will contain all patients who provide informed consent for this study.

5.2. Full Analysis Set

The Full Analysis Set (FAS) comprises all patients assigned to treatment, who received at least 1 full or partial dose of IMCgp100. The FAS will be used for all demography, baseline characteristics, and OS data summaries.

5.3. Safety Analysis Set [SAF]

The Safety Analysis Set (SAF) includes all patients who have received at least 1 full or partial

[REDACTED]

dose of IMCgp100. The safety analysis set will be used for the safety summary of the study.

6. General Considerations

6.1. Reference Start Date and Study Day

Study Day will be calculated from the reference start date and will be used to show start/stop day of assessments and events.

Reference start date is defined as the day of the first dose of rollover study drug, (Day 1).

If the date of the event is on or after the reference start date, then:

- Study Day = (date of event – reference start date) + 1.

If the date of the event is prior to the reference start date, then:

- Study Day = (date of event – reference start date).

In the situation where the event date is partial or missing, the date will appear partial or missing in the listings, and Study Day and any corresponding durations will appear as missing in the listings.

Please note for survival, the first dose of the parent study will be used as reference instead.

6.2. Baseline

Unless otherwise specified, baseline is defined as the last non-missing measurement (including unscheduled assessments) taken prior to the first dose of rollover treatment received (i.e., Rollover Cycle 1 Day 1 RC1D1 pre-dose). In the case where the date of the last non-missing measurement and the first dose date of rollover treatment coincide, that measurement will be considered pre-dose and included in the baseline calculation as appropriate. This will be the rule for demography, other baseline characteristics (including disease status), laboratory data, and physical examination data. For ECGs and vital signs, where the time of assessment is recorded, if the last non-missing measurement and the reference start date coincide, then only if the time of the measurement is prior to the time of first dose will the measurement be considered pre-dose and included in the baseline calculation. Furthermore, because ECGs are supposed to be taken pre-dose on RC1D1, any RC1D1 measurements of ECGs with a time on or after the time of first dose will be queried with Data Management.

Note that baseline measurements made in the rollover study will only be used for summarizing baseline demographic information and disease characteristics. It will not be used for analyzing change from baseline, as comparisons to these baseline values cannot take into account the fact that patients were already taking IMCgp100 in their parent study.

6.3. Retests, Unscheduled Visits and End of Treatment Data

In general, for by-visit summaries, data recorded at the nominal or observed visit will be presented. Unscheduled measurements will not be included in by-visit summaries, but will

contribute to the baseline value, or best/worst case value where required.

In the case of a retest (same visit number assigned), the earliest available measurement for that visit will be used for by-visit summaries. For best/worst case, all available measurements including retest values will be used.

End of Treatment (EOT) visits will be summarized together in the by-visit summaries.

Listings will include scheduled, unscheduled, retest and early discontinuation data.

6.4. Windowing Conventions

There will be no post-hoc visit windowing for the analyses performed for this study. All data will be organized and analyzed according to the scheduled visit times (allowing for ± 7 days) as outlined in the Protocol Section 7-1 and by the visit denoted on the eCRF.

6.5. Statistical Tests

There will be no formal statistical hypotheses testing.

6.6. Software Version

All analyses will be conducted using SAS version 9.4 or higher.

7. Statistical Considerations

7.1. Adjustments for Covariates and Factors to be Included in Analyses

Not applicable in this study.

7.2. Multicenter Studies

This study will be conducted by multiple investigators at multiple centers internationally. However, no summaries by country or center will be completed for this study.

7.3. Missing data

Missing data will not be imputed.

7.4. Multiple Comparisons/ Multiplicity

Not applicable.

7.5. Examination of Subgroups

No subgroups will be defined for this study.

8. Output Presentations

[APPENDIX 1](#) shows conventions for presentation of data in outputs.

The template shells provided with this SAP describe the presentations for this study and therefore the format and content of the summary tables, figures, and listings to be provided by

IQVIA Biostatistics.

9. Disposition and Withdrawals

All patients who provide informed consent will be accounted for in this study. Any subjects who signed the informed consent, but never started the study treatment for any reason will be regarded as screen failures. For these patients, the eCRF data collected will not be included in summary analyses but will be reported in the CSR as part of the listings.

Patient disposition and discontinuation/withdrawals will be presented for the All Patients Enrolled (ENR) set. Important protocol violations will be listed for the Full Analysis Set (FAS).

10. Demographic and other Baseline Characteristics

Demographic data and other baseline characteristics will be presented for the FAS.

The following demographic and other baseline characteristics will be listed for this study:

1. Demography
 - Age (years)
 - Sex
 - Is the patient of child bearing potential? (females only)
 - Race
 - Ethnicity
 - Country
 - Weight (kg)
 - Height (cm)
 - BMI (kg/m²)
2. Disease data
 - Diagnosis and extent of cancer (disease at baseline)
 - Prior anti-cancer therapy

10.1. Derivations

- Age (years) will be derived using the following SAS code:

$$\text{floor} \left(\frac{(\text{intck}('month', \&birth, \&date) - (\text{day}(\&date) < \text{day}(\&birth)))}{12} \right)$$
 - &birth= Date of birth

- &date = (Date of informed consent)
- Note: For countries where only the year of birth is provided due to privacy laws, impute birth month and day as June 15.
- Time since primary diagnosis (years) = (Date of informed consent – Date of Primary Diagnosis + 1) / 365.25
 - Note: Partial primary diagnosis dates are imputed using 15th day of month if only month/year present or July 02 if only year present.
- Best response on any prior anti-cancer therapy for metastatic disease = the “best” *best response* as derived from the *Prior Anti-Cancer Therapy (PAT)* eCRF page, considering all medications identified from the medical review. From best to worst, the following order will be used:
 - Complete Response
 - Partial Response
 - Stable Disease
 - Progressive Disease
 - Non-Evaluable
 - Not Applicable
- BMI (kg/m²) = weight (kg) / (height (cm) / 100)²

11. Surgical and Medical History

Medical History information will be listed only.

- Medical History will be coded using Medical Dictionary for Regulatory Activities (MedDRA) central coding dictionary, using the latest version of MedDRA available at the time of coding for the reporting period.
 - Medical History conditions are defined as those conditions beginning prior to screening which stop prior to or are ongoing at Screening.
 - Presented by System Organ Class (SOC) and Preferred Term (PT).

12. Concomitant Medications

Concomitant medications and significant non-drug therapies will be presented and coded using the World Health Organization drug dictionary (WHODD), using the latest version available at the time of coding for the reporting period.

Medications will be listed by Preferred Name (coded) and by Reported Term.

See [APPENDIX 2](#) for handling of partial dates for medications. In the case where it is not possible to define a medication as prior, concomitant, or post treatment, the medication will be classified by the worst case; i.e. concomitant. (Refer to Protocol Section 6.2)

- ‘Prior’ medications are medications which started and stopped prior to the first dose of study drug of the rollover study.
- ‘Concomitant’ medications are medications which:
 - started prior to, on or after the first dose of study drug of the rollover study and started no later than the last dose of study drug of this rollover study,
 - AND ended on or after the date of first dose of study drug of the rollover study or were ongoing at the end of the rollover study.
- ‘Post’ medications are medications which started after the last dose of study drug of this rollover study.

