**Table 6-2 Recommended Dose Modifications by Toxicity Grade for Study Medications**

Worst Toxicity NCI CTCAE v4.03 Grade	Recommended Dose Modifications
Skin Toxicity	
Rash/Photosensitivity	
Grade 1	Continue dosing. If symptomatic, consider systemic antihistamine regimen
Grade 2	Hold all doses of study IMCgp100 until returned to NCI CTCAE grade $\leq$ 1. Use local skin management and systemic antihistamine regimen as indicated. Anti-pruritic regimen: Can include antihistamine therapy. In patients where antihistamine therapy does not provide adequate relief, gabapentin or aprepitant may be considered. Topical corticosteroid regimens: Preparation of recommended regimens 
 
• For face and/or intertriginous areas (including genitalia) recommend alclometasone 0.05% or hydrocortisone 2.5% creams
 
• For other body areas (ie, trunk and extremities) recommend clobetasol or betamethasone 0.05% creams. Consider spray preparation for ease of application on trunk. For scalp involvement, consider a foam preparation
 

Grade 3	Hold all doses of IMCgp100 until returned to NCI CTCAE grade $\leq$ 1.

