**Table 6-2 Recommended Dose Modifications by Toxicity Grade for Study Medications**

Worst Toxicity NCI CTCAE v4.03 Grade	Recommended Dose Modifications
Grade 2	Intravenous fluid support and other supportive measures for additional AE as needed.
Grade 3 or 4	Hold all doses of IMCgp100 until returned to NCI CTCAE grade $\leq$ 1. Intravenous fluid support and other supportive measures for additional adverse events. In cases of hypotension where fluid support is not adequate, consider systemic corticosteroid therapy as needed for hypotension. In case of hypotension not responding to intravenous corticosteroid, inotropic pressor support may be indicated.
Cytokine Release Syndrome	
Grade 2	Interrupt infusion of IMCgp100. Supportive measures for symptoms of cytokine release, ie, intravenous fluid support, non-steroidal anti-inflammatory drug (NSAID), antihistamine. If resolves within 4 hours, may restart infusion of IMCgp100. If recurs with restarting infusion, hold the dose of IMCgp100 and institute supportive measures as indicated.
Grade 3	Discontinue infusion immediately. Supportive measures for symptoms of cytokine release, ie, intravenous fluid support, NSAID, antihistamine. To consider intravenous corticosteroid (eg, methylprednisolone or hydrocortisone) for severe symptoms and management of sequelae. If symptoms resolve to NCI CTCAE grade 1 within 7 days, may consider restarting IMCgp100 after written approval of Sponsor Medical Monitor.
Grade 4	Discontinue infusion immediately. Supportive measures for symptoms of cytokine release. In addition to supportive measures, intravenous corticosteroid dosing (eg, methylprednisolone or hydrocortisone) should be administered. If symptoms do not resolve with intravenous corticosteroid dosing consider anti-IL6 (tocilizumab) therapy. If symptoms resolve to NCI CTCAE grade 1 within 7 days, may consider restarting IMCgp100 after written approval of Sponsor Medical Monitor.
Other Adverse Events	
In patients experiencing adverse events (not meeting the specific criteria above) of grade $\geq$ 3, study drugs should be omitted until resolved to grade $\leq$ 1. Treat according to institutional practice and for immune-related adverse events of grade 3 or greater, treatment with corticosteroids should be considered. Consult Sponsor Medical Monitor for further guidance as needed.	

NCI CTCAE = National Cancer Institute Common Terminology Criteria for Adverse Events; NSAID = non-steroidal anti-inflammatory drug.

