### 9.4 Treatment Data

Actual dose and duration in days of treatment for IMCgp100, as well as the dose intensity (actual dose received/actual duration), and relative dose intensity (the ratio of dose intensity to planned dose/planned duration) will be summarized by descriptive statistics

Concomitant medications and significant non-drug therapies prior to and after the start of the study treatment will be listed by patient and summarized by anatomical therapeutic chemical term.

The reason for discontinuation from treatment will be summarized and listed, along with dates of first and last doses, duration of exposure to each study drug, and date of discontinuation for each patient.

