12.1. Prohibited Concomitant Medications/Therapies

During the ‘concomitant’ period of the study (as above), patients may not receive other additional investigational drugs, agents, devices, chemotherapy, or any other therapies that may be active against cancer. While systemic corticosteroid therapy will interfere with the mechanism of action of the study drugs, its use is recommended in some settings. See Protocol Section 6.2.3 for further details.

Medications/therapies that are prohibited will be flagged in the listing of concomitant medications. These will be identified using a medically-approved list of Preferred Names provided by the Sponsor. See [APPENDIX 2](#) for handling of partial dates for concomitant alternative cancer therapies under Algorithm for Prior / Concomitant Medications.

13. Study Drug Exposure

All information relevant to exposure will be calculated from Rollover Cycle 1 Dose 1 (RC1D1), unless otherwise noted. Number of cycles, duration of dose on rollover study in days, duration of dose from first parent study in days, total actual dose received in rollover, dose intensity in rollover, relative dose intensity will be summarized for IMCgp100. Tolerability of study treatment will be assessed by summarizing the number of treatment dose interruptions. Reasons for dose interruptions will be listed.

The SAF analysis set will be used for presenting all exposure and tolerability variables.

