	Partial	Impute start date as earliest possible date (i.e. first day of month if day unknown or 1 st January if day and month are unknown) and impute stop date as latest possible date (i.e. last day of month if day unknown or 31 st December if day and month are unknown), then: If stop date < study drug start date, assign as prior If stop date ≥ study drug start date and start date ≤ end of treatment, assign as concomitant If stop date ≥ study drug start date and start date > end of treatment, assign as post treatment
	Missing	Impute start date as earliest possible date (i.e. first day of month if day unknown or 1 st January if day and month are unknown), then: If stop date is missing could never be assumed a prior medication If start date ≤ end of treatment, assign as concomitant If start date > end of treatment, assign as post treatment

START DATE	STOP DATE	ACTION
Missing	Known	If stop date < study drug start date, assign as prior If stop date ≥ study drug start date, assign as concomitant Cannot be assigned as 'post treatment'
	Partial	Impute stop date as latest possible date (i.e. last day of month if day unknown or 31 st December if day and month are unknown), then: If stop date < study drug start date, assign as prior If stop date ≥ study drug start date, assign as concomitant Cannot be assigned as 'post treatment'
	Missing	Assign as concomitant

Note: Study drug start date is the parent study first drug date.

Document Approval Signature(s)

This document has been signed electronically in compliance with IQVIA and IQVIA Companies' electronic signature policies and procedures. This page is a manifestation of the electronic signatures, which may be confirmed within the IQVIA and IQVIA Companies' source system in accordance with IQVIA and IQVIA Companies' records retention policies.

Note: the Title field in the signature block has been intentionally left blank.

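### SAP Appendix 2 dates concomitant medication from the first parent-study dose while SAP Section 12 dates it from the first rollover dose, and the protocol's summary by ATC term is absent from the SAP without being declared removed

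*SAP*

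**What the plan says.** **Anchor date.** SAP Section 12 calls a medication prior if it both started and stopped before the first rollover dose. To be concomitant, it must have ended on or after that dose (or still be ongoing at the end of the rollover study) and have started no later than the last rollover dose. Appendix 2 gives a separate algorithm that compares stop dates with a study drug start date and closes with "Note: Study drug start date is the parent study first drug date".

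**Summary.** Protocol 9.4 says that concomitant medications and significant non-drug therapies "will be listed by patient and summarized by anatomical therapeutic chemical term". SAP Section 12 says "Medications will be listed by Preferred Name (coded) and by Reported Term" and names no table and no ATC level. SAP 3.3, the place for departures from the protocol, contains one item: "Tables/Listings for change from baseline and shift tables are removed from the analysis for vital signs and ECG data".

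**Prohibited flag.** SAP 12.1 marks prohibited drugs within the listing of concomitant medications. "These will be identified using a medically-approved list of Preferred Names provided by the Sponsor". It states no criterion of route, indication or date. It does acknowledge that systemic corticosteroids are recommended in some settings, and it points to Protocol 6.2.3.

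**The concern.** A programmer cannot follow both anchor rules. In a rollover study the two dates are far apart by design: Protocol 2.1 requires at least 4 weeks of tolerated dosing before entry, so they are separated by about 4 × 7 = 28 days at the least, and possibly by years. If Appendix 2 is programmed as written, treatment given and finished in the parent study appears as concomitant with rollover dosing and can be flagged there as prohibited.

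The missing summary matters because long-term safety and tolerability is a secondary objective and medication use is part of the supporting description. The SAP text plans no patient counts by drug class, and a reader comparing protocol and SAP would find no record of the decision.

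The flag is a smaller matter. For Grade 2 rash, Protocol Table 6-2 reads "recommend alclometasone 0.05% or hydrocortisone 2.5% creams"; for Grade 3 cytokine release syndrome it reads "To consider intravenous corticosteroid (eg, methylprednisolone or hydrocortisone) for severe symptoms and management of sequelae". The drug name hydrocortisone covers both, so a name alone cannot separate route or setting.

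**Working it through.** There is no sample size, power or error-rate figure to reproduce. The check sets the two rules side by side and applies both to the same records.

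**Notation.** P is the first parent dose, R the first rollover dose and L the last rollover dose; s and e are a medication's start and stop dates.

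- SAP Section 12: post if s > L; prior if e < R; otherwise concomitant.
- Appendix 2, both dates known: prior if e < P; otherwise concomitant if s ≤ L, and post if s > L.

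**Assumptions.** P = day 0; R = day 28, 180, 365 or 730; L = R + 200. Appendix 2's end of treatment is taken as the last dose.

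| Record (start to stop day) | SAP Section 12 | Appendix 2 |
|---|---|---|
| −60 to −10, stopped before parent study | prior | prior |
| −10 to 10, stopped during parent study | prior | concomitant |
| 5 to 20, wholly within parent study | prior | concomitant |
| 10 to R + 5, ongoing into rollover | concomitant | concomitant |
| R + 10 to R + 15, on rollover | concomitant | concomitant |
| L + 5 to L + 10, after last dose | post | post |

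The result is the same at all four values of R.

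**Full grid.** Every start/stop pair in 5-day steps was classified both ways, with starts from 50 days before P to about 50 days after L.

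| R (day) | Pairs | Disagreements |
|---|---|---|
| 28 | 2,343 | 81 |
| 180 | 4,848 | 1,026 |
| 365 | 9,177 | 3,431 |
| 730 | 21,733 | 12,191 |

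Every disagreement went from prior to concomitant, and none lay outside P ≤ e < R. The counts locate the conflict; they are not rates, because real medication dates are not spread over a grid.

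**After the change.** Put R in place of P in Appendix 2. A drug with s > L has e ≥ s > L ≥ R, so it cannot be prior and both rules call it post. Otherwise both call it prior when e < R and concomitant when e ≥ R. The rules then agree on every record.

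**Summary.** Protocol 9.4 promises a listing and an ATC summary; SAP Section 12 names the listing only; SAP 3.3 does not mention medications. The SAP does say that data will be summarized where it plans a summary, for example for exposure (Section 13) and hematology (15.3).

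**The case against.** Several points can be made for the plan.

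- **Section 12's own definitions are sound.** It refers to Appendix 2 only for partial dates, which is also that appendix's title, and nothing says that the appendix overrides the section. This stands as far as it goes: the fault lies in the appendix note. But the algorithm has rows for fully known dates, so the contradiction is not confined to partial ones.
- **Nothing on rollover is lost.** A reader might infer that rollover use of rescue or prohibited drugs can no longer be read from the outputs. The documents do not support that. Such use is concomitant under both rules, it stays in the listing, and recorded dates allow parent-study courses to be told apart.
- **The size is unknown.** A reader might divide parent time by total time and get 2/(2 + 1) = 67% for two years on parent and one on rollover, or 1/(1 + 1) = 50% for one year on each. Those durations are invented, and the sum also assumes evenly spread short courses and complete entry of parent-study drugs in the rollover database. Protocol Table 7-1 collects prior and concomitant medications at Screening without a look-back, and Protocol 7.1 places parent-study assessments in the parent database.
- **The shells may contain the table.** SAP Section 8 leaves table content to shells that are not in the documents. An ATC table could be there, but the SAP text would still need to say so.
- **The flag may work adequately.** A reader might infer that it errs in both directions. That depends on a Sponsor list that is not in the documents and on redacted text in Protocol 6.2.3. The list is medically approved, and SAP 12.1's pointer to Protocol 6.2.3 covers the classes that its own restatement leaves out. What stands is only that no route, indication or date criterion is stated.
- **Tolerability is defined otherwise.** Protocol 4.4 defines it by dose interruptions, reductions and dose intensity. A new table of rescue drugs would be a preference, not something the protocol promised.

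**Conclusion.** Two discrepancies hold on the text. First, SAP Section 12 and the Appendix 2 medication algorithm use different anchor dates. Following Appendix 2 turns every recorded drug stopped on or after the first parent dose and before the first rollover dose from prior into concomitant, and exposes it to the prohibited flag. The effect runs in one direction only, and its frequency depends on how many parent-study courses are entered, which the documents do not tell. Second, the ATC summary in Protocol 9.4 is not named in SAP Section 12 and not declared as removed in SAP 3.3, subject to what the shells contain.

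The reliance on Preferred Name for the prohibited flag is a minor weakness. The flag marks a listing, and the documents describe no count built on it. Neither the incidence of adverse events nor overall survival is affected; the consequence is limited to the description of medication use.

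**What to change.** 1. In the note under the Appendix 2 medication algorithm, replace the parent-study date with the date of the first rollover dose, so that it matches SAP Section 12. This changes one line.
2. Restore the ATC summary of concomitant medications in SAP Section 12, or record its removal, with a reason, in SAP 3.3. The cost is one standard table or one sentence. Protocol 10.4 already provides for coding based on the ATC classification.
3. As a minor addition, state that records flagged by Preferred Name will be medically reviewed for date, route and indication against the full Protocol 6.2.3. The documents do not confirm that the medication eCRF holds route and indication, so check this first.
4. Reconcile Protocol 6.2.3, Protocol Table 6-2 and SAP 12.1 on which corticosteroid and antibody uses count as prohibited. The visible text of 6.2.3 bars immunosuppressives and other therapeutic monoclonal antibodies, while Table 6-2 includes corticosteroids and tocilizumab in toxicity management. Exceptions may be in redacted text. Which rule applies is for the sponsor to settle.
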